### 3. Objectives, Endpoints, and Estimands

Objectives	Endpoints
Primary	

 
To assess the effect of lebrikizumab 250 mg Q2W in reducing the signs and symptoms of AD in participants with moderate-to-severe AD and skin of color
 
	
 
Percentage of participants achieving EASI-75 (<math>\geq 75\%</math> reduction from baseline in EASI) at Week 16
 

Secondary	

 
To evaluate the effect of treatment with lebrikizumab in the signs and symptoms of AD and health outcome measures, in participants with moderate-to-severe AD and skin of color
 
	
 
Percentage of participants achieving EASI-75 at Week 24
 
Percentage of participants with an IGA score of 0 or 1 and a reduction <math>\geq 2</math> points from baseline to Weeks 16 and 24
 
Percentage change in EASI total from baseline to Weeks 16 and 24
 
Change in EASI total from baseline to Weeks 16 and 24
 
Percentage of participants achieving EASI 90 at Weeks 16 and 24
 
Percentage of participants with a Pruritus NRS of <math>\geq 4</math> points at baseline who achieve a 4-point reduction at Weeks 16 and 24
 
Percentage of participants with a Pruritus NRS <math>\geq 3</math> points at baseline who achieve at least 3-point reduction at Weeks 16 and 24
 
Percentage change in Pruritus NRS score from baseline to Weeks 16 and 24
 
Percentage of participants with a Sleep-Loss Scale score of <math>\geq 2</math> points at baseline who achieve a 2-point reduction at Weeks 16 and 24
 
Percentage change in Sleep-Loss Scale score from baseline to Weeks 16 and 24
 
Percentage of participants with a Skin Pain NRS of <math>\geq 4</math> points at baseline who achieve a 4-point reduction from baseline to Weeks 16 and 24
 
Change in POEM from baseline to Weeks 16 and 24
 
Change in DLQI from baseline to Weeks 16 and 24 for participants <math>\geq 16</math> years of age at baseline
 

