	
 
• Change in cDLQI from baseline to Weeks 16 and 24 for participants <16 years of age at baseline
 
• Percentage of participants with a DLQI of <math>\geq 4</math> points at baseline who achieve a <math>\geq 4</math>-point improvement in DLQI at Weeks 16 and 24 for participants <math>\geq 16</math> years of age at baseline
 

Exploratory
	

 
• To evaluate the efficacy and health outcome measures of lebrikizumab from baseline by visit in participants with skin of color and moderate-to-severe AD
 
	
 
• Percentage change in PO-SCORAD from baseline by visit
 
• Change in Post-inflammatory Dyschromia Scale from baseline by visit
 
• Percentage change in ADCT from baseline by visit
 
• Using WPAI-AD by visit, change in baseline in             
 
○ absenteeism in those who are currently employed (working for pay)
 
○ presenteeism in those who are currently employed (working for pay)
 
○ overall work impairment in those who are currently employed (working for pay), and
 
○ impairment in activities (all participants)
 
 
 
• Percentage of participants with an F-IGA score of 0 or 1 and a reduction <math>\geq 2</math> points from baseline by visit
 
• Lichenification change from baseline (calculated from EASI)
 
• Participant satisfaction change from baseline (1 question)
 
• Percentage of participants achieving EASI-75 by visit
 
• Percentage of participants with an IGA score of 0 or 1 and a reduction <math>\geq 2</math> points from baseline by visit
 
• Percentage change in EASI total by visit
 
• Change in EASI total by visit
 
• Percentage of participants achieving EASI-90 by visit
 

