#### Type of Participant and Disease Characteristics

2. Participants who are self-reported race other than White, including but not limited to persons who self-identify as Black or African American, American Indian or Alaska Native, Asian, Native Hawaiian, or Other Pacific Islander.
3. Participants who are Fitzpatrick phototype IV-VI (Section 8.1.15).
4. Have chronic AD (according to American Academy of Dermatology Consensus Criteria; Eichenfield et al. 2014; Appendix 7, Section 10.7) that has been present for  $\geq 1$  year before screening visit.
5. Have EASI  $\geq 16$  at the baseline visit.
6. Have Investigator's Global Assessment (IGA) score  $\geq 3$  (scale of 0 to 4) at the baseline visit.
7. Have  $\geq 10\%$  BSA of AD involvement at the baseline visit.
8. Have a history of inadequate response to treatment with topical medications; or determination that topical treatments are otherwise medically inadvisable.

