### **8.1.4. Face-Investigator's Global Assessment (F-IGA)**

The F-IGA is an investigator-administered, single-item scale that rates the severity of the participant's AD on the face. The F-IGA is composed of a 5-point scale ranging from 0 (clear) to 4 (severe), and a score is selected using descriptors that best describe the overall appearance of the facial lesions at a given time point.

Assessors must be trained and certified by the sponsor prior to conducting this assessment. A single assessor should be assigned to each participant for as many visits as possible to avoid inter-assessor variability in scoring. The recall period of this assessment is present time.

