5.1.1 Analysis Populations

Analysis populations are defined in Table KGBP.5.1 along with the analyses they will be used to conduct. The number of patients included in each population will be summarized.

Table KGBP.5.1.1 Analysis Populations

Population	Description
All Entered Patients	All patients who signed informed consent. Patient flow will be summarized.
Intent-to-Treat (ITT) Population	All enrolled patients according to their planned intervention. Unless otherwise specified, efficacy and health outcomes analyses for Weeks 0 to 16 of the Treatment Period will be conducted on this population.
Safety Population	All enrolled patients who received at least 1 confirmed dose of lebrikizumab 250 mg. Safety analyses will be conducted on this population.
Treatment Period II Population	All enrolled patients who received at least 1 confirmed dose of lebrikizumab 250 mg during Weeks 16 to 24 of the Treatment Period. Unless otherwise specified, efficacy and health outcomes analyses for Weeks 16 to 24 of the Treatment Period will be conducted on this population.

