5.11 Efficacy Analyses

Table KGBP.5.4 includes the description and derivation of the efficacy measures and endpoints.

For categorical parameters, the number and percentage of patients in each category will be presented, as well as a 90% Wilson-Score confidence interval for the percentage. For continuous parameters, descriptive statistics will include n (number of patients), mean, standard deviation, Q1, median, Q3, minimum, and maximum. These summaries will be provided for the data as-observed and after implementation of LOCF and MCMC-MI imputation as described in Sections 5.4.2 and 5.4.3.

The IGA, F-IGA, EASI, BSA, Pruritus NRS, Skin Pain NRS, and Sleep-Loss Scale will be reported by clinic visit.

Table KGBP.5.4. Description and Derivation of Efficacy/Health Outcomes Measures and Endpoints

Measure	Description	Variable	Derivation/Comment	Imputation Approach if Missing Components
Investigator's Global Assessment (IGA)	The IGA is a static assessment and rates the severity of a patient's AD. The IGA is comprised of a 5-point scale ranging from 0 (clear) to 4 (severe), and a score is selected using descriptors that best describe the overall appearance of the lesions at a given time point.	IGA score	Single item. Range: 0-4 0 represents "clear" 4 represents "severe"	Single item, missing if missing
		• IGA (0,1) with ≥ 2 -point improvement ^a IGA (0)	• Observed score of 0 or 1 and change from baseline ≤ 2 Observed score of 0	Missing if baseline or observed value is missing Single item, missing if missing
Face-Investigator's Global Assessment (F-IGA)	The F-IGA is a static assessment and rates the severity of a patient's AD on the face. The F-IGA is comprised of a 5-point scale ranging from 0 (clear) to 4 (severe), and a score is selected using descriptors that best describe the overall appearance of the lesions at a given time point.	F-IGA Score	Single item. Range: 0-4, 0 represents "clear", 4 represents "severe"	Single item, missing if missing
		F-IGA (0,1)	Observed score of 0 or 1	Missing if baseline or observed value is missing
		F-IGA (0)	Observed score of 0	Single item, missing if missing

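### The F-IGA responder endpoint has no baseline facial-disease restriction, so participants with a clear or almost clear face distort the rate: downward under the listed definition, upward under the SAP derivation

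*Protocol*

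**What the plan says.** **Endpoint definition.** Protocol Section 3 lists, among the exploratory endpoints, "Percentage of participants with an F-IGA score of 0 or 1 and a reduction" of at least 2 points from baseline, by visit. SAP Table KGBP.3.1 repeats it. Neither sets a minimum baseline F-IGA.

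**Scale.** Protocol Section 8.1.4: "The F-IGA is composed of a 5-point scale ranging from 0 (clear) to 4 (severe").

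**Derivation.** SAP Section 5.11, Table KGBP.5.4, derives F-IGA (0,1) as "Observed score of 0 or 1" and stops there. The whole-body IGA row just above it reads "Observed score of 0 or 1 and change from baseline", followed by a 2-point condition.

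**Entry.** Protocol Section 5.1 requires EASI of at least 16, a whole-body score ("Have Investigator's Global Assessment (IGA) score") of at least 3, and at least 10% "BSA of AD involvement at the baseline visit". No criterion concerns the face.

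**Population.** SAP Section 5.1.1 says of the ITT population, which is all enrolled patients: "Unless otherwise specified, efficacy and health outcomes analyses for Weeks 0 to 16 of the Treatment Period will be conducted on this population". The Week 16 to 24 population is everyone dosed in that period. Nothing specifies a subset for F-IGA.

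**Contrast.** Other point-reduction endpoints in Protocol Section 3 do carry a baseline minimum. Pruritus NRS, for example, is restricted to those with at least 4 "points at baseline who achieve a 4-point reduction at Weeks 16 and 24". Skin Pain NRS, Sleep-Loss and DLQI are restricted in the same way.

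**The concern.** A participant whose face is clear or almost clear at baseline has no 2-point improvement left to make. If such participants are counted, the percentage mixes two things: how well facial eczema responds, and how many participants had facial eczema at the start.

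The plan protects its other Section 3 point-reduction endpoints against this. The symptom and DLQI endpoints have a baseline minimum, and whole-body IGA is protected because entry requires a score of at least 3. F-IGA has neither protection.

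F-IGA is one of the novel endpoints named in the study rationale (Protocol Sections 1.1 and 2.1), so the figure is likely to be read as a facial response rate. The two documents also point in opposite directions on how the affected participants are classified, so a reader could not tell which way the reported figure is off.

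**Working it through.** **Inputs from the documents.** F-IGA is scored 0 to 4. Planned enrolment is about 95, and the precision table uses 80. Percentages carry a two-sided 90% Wilson interval. The only planning response rate is about 50%, and it is for EASI-75.

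**Assumed inputs** (not in the documents):
- f, the share observed at a visit who had baseline F-IGA 0 or 1: 10% to 50%.
- r, the response rate among those with baseline F-IGA of at least 2: 40% to 60%.
- s, the share of the f group scoring 0 or 1 at the visit: 0.9 to 1.

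**Step 1: the plan's own precision figure.** The Wilson half-width is h = z√(p(1−p)/n + z²/4n²) / (1 + z²/n), with z = 1.645. At p = 0.50 and n = 80, h = 9.04 points, giving 40.96% to 59.04%. This matches Protocol Section 9.5 and SAP Table 4.2. It confirms the interval method used in Step 4 but does not bear on the F-IGA definition.

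**Step 2: which scores count as response.**

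| Baseline F-IGA | Protocol Section 3 / Table KGBP.3.1 | Table KGBP.5.4 |
|---|---|---|
| 0 | none | 0, 1 |
| 1 | none | 0, 1 |
| 2 | 0 only | 0, 1 |
| 3 | 0, 1 | 0, 1 |
| 4 | 0, 1 | 0, 1 |

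Under the listed definition, baseline 0 or 1 is a non-response at every visit, even if the face stays clear throughout. Under Table KGBP.5.4, the same participant is a responder simply by staying at 0 or 1.

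**Step 3: effect on the rate.**
- Listed definition: rate = r(1 − f).
- Table KGBP.5.4: rate = r(1 − f) + s·f.
- Gap between the two: s·f.

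With r = 50%:

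| f | Listed definition | Table KGBP.5.4, s = 1 | Table KGBP.5.4, s = 0.9 |
|---|---|---|---|
| 10% | 45% | 55% | 54% |
| 30% | 35% | 65% | 62% |
| 50% | 25% | 75% | 70% |

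For example, at f = 30%: 0.50 × 0.70 = 35%, and 35% + 30% = 65%. Across r = 40% to 60% and f = 10% to 50%, the listed definition shifts the rate by −4 to −30 points and the SAP derivation by +3 to +30 points.

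Here r is held equal under both rules. Table KGBP.5.4 also counts a move from 2 to 1, so its own r could be higher, never lower.

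**Step 4: cost of restricting the denominator.** With n = 95 and a 50% response, the half-width is 8.3 points for all participants. It becomes 8.7 points at f = 10% (n = 86), 9.9 at f = 30% (n = 66) and 11.5 at f = 50% (n = 48).

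**Step 5: which definition was meant.** In Table KGBP.5.4, F-IGA (0,1) is set to missing if the baseline value is missing, while F-IGA (0) depends only on the observed value. Needing the baseline makes sense only if a change condition was intended. That favours the Protocol definition, but it is an inference; the derivation as written has no such condition.

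**The case against.** Several points on the other side stand.

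- **Direction.** A reader might infer from the endpoint list alone that the reported facial response rate will be biased downward. The documents do not support that. Table KGBP.5.4 is the derivation to be programmed, and as written it pushes the rate up. The direction is open until the two are reconciled.
- **Uniqueness.** A reader might also infer that F-IGA is the only unprotected point-reduction variable. That is true of the Protocol Section 3 endpoints. However, Table KGBP.5.4 also derives CDLQI and POEM 4-point improvements with no baseline minimum.
- **Subgroups.** It is tempting to say that subgroup comparisons of F-IGA would be misleading. None is planned: SAP Section 5.14 covers EASI-75 at Week 16, and Protocol Section 9.3.6.1 covers the primary and some secondary endpoints. The SAP allows additions, so this is a possibility only.
- **Target.** A percentage over all participants is a well-defined quantity. Restricting to those with facial disease changes the target; it does not correct a miscalculation. The change is still worthwhile, because the all-participant figure does not answer how facial eczema responds.
- **Visibility.** F-IGA is summarised at baseline (SAP Section 5.8.1). If that summary is by category, a reader could see f and rescale approximately. Under an as-observed analysis, though, f can change from visit to visit.
- **Size.** Protocol Section 2.2 says lesions often affect the face and neck, so f may be small. Nothing in the documents fixes it.

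None of this supplies the missing restriction or removes the conflict between the definitions.

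**Conclusion.** The concern holds in this form: no baseline facial-disease restriction exists, entry does not require facial involvement, and participants with baseline F-IGA 0 or 1 distort the rate under either definition. Under Protocol Section 3 and SAP Table KGBP.3.1 they are non-responders by construction, and the rate is (1 − f) times the rate in those with facial disease. Under Table KGBP.5.4 they are near-automatic responders and the rate is inflated.

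The structural finding follows from the documents alone. Its size does not, because f, r and s are all assumptions. The 35% versus 65% contrast illustrates one combination and does not predict the trial's result.

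Severity is low. This is one exploratory endpoint in a single-arm, descriptive study with no hypothesis test. The primary endpoint, the safety analyses and the Week 16 dosing assignment do not depend on F-IGA.

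**What to change.** 1. In SAP Table KGBP.5.4, add the reduction of at least 2 points to the F-IGA (0,1) derivation so that it agrees with Protocol Section 3 and SAP Table KGBP.3.1.
2. In all three places, restrict the endpoint. Suggested wording: *Percentage of participants with F-IGA of at least 2 at baseline who achieve F-IGA 0 or 1 and a reduction of at least 2 points, by visit.* A baseline of 2 is the lowest from which the criterion can be met.
3. Report the denominator at each visit and the number excluded for baseline F-IGA 0 or 1.
4. State in a footnote that participants at baseline 2 must reach 0, while those at 3 or 4 may respond with 0 or 1. The restriction does not remove this uneven bar.

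The cost is one filter on data already collected at baseline, edits to two SAP tables and one line of Protocol Section 3, and a smaller denominator. Under Protocol Section 9.3.1, a change to analysis methods needs an amendment only if it alters a principal feature; other changes are justified in the clinical study report. The sponsor would need to judge whether the Protocol wording can wait for another amendment. The loss of precision is modest: at n = 95, 50% response and f = 30%, the 90% half-width rises from 8.3 to 9.9 points.

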**Primary estimand**

The primary clinical question of interest is: What is the intervention effect in percentage of participants achieving at least 75% improvement from baseline in EASI-75 after 16 weeks of lebrikizumab 250 mg Q2W intervention in participants with skin of color and moderate-to-severe AD who remain on study treatment until Week 16.

The estimand is described by the following attributes:

Population: participants with skin of color and moderate-to-severe AD who met inclusion and exclusion criteria and who remained on study treatment until Week 16. Further details can be found in Section 5.

Endpoint: whether participants achieve at least 75% improvement from baseline in EASI at Week 16.

Intercurrent events: There are no intercurrent events for this population since participants who initiate rescue medication are discontinued from the study and hence study treatment. Therefore, participants who stay on study treatment through Week 16 will not have an intercurrent event such as initiating rescue medication or permanently discontinuing treatment. Further details on

study interventions and concomitant medications, including rescue treatments, can be found in Section [6.8.1](#).

Population-level summary: percentage of participants achieving EASI 75 response at Week 16.

**Secondary estimand(s)**

There is no secondary estimand planned at this stage; however, additional estimands might be specified in the statistical analysis plan (SAP).

## 4. Study Design

### 4.1. Overall Design

Study J2T-MC-KGBP (KGBP) is a single group treatment, open-label, Phase 3b study, which is 24 weeks in treatment duration. The study is designed to evaluate the safety and efficacy of lebrikizumab in adolescent and adult participants with skin of color and moderate-to-severe AD.

#### Study Periods

This trial has 3 study periods:

- Screening (Visit 1: ≤30 days prior to baseline)
- Treatment (Visits 2-9: 24 weeks)
- Safety follow-up (Visit 801: approximately 12 weeks after last treatment)

#### Visit Types

Study visits at Week 12 (Visit 6) and Week 20 (Visit 8) will be performed virtually, that is, via telephone or telemedicine tools.

All other visits will be conducted at the clinical trial site.

#### Dosing

During the 24-week Treatment Period, approximately 95 participants will receive treatment:

- 500 mg subcutaneous (SC) once every 2 weeks (Q2W) loading dose at baseline and Week 2, followed by 250 mg SC Q2W until Week 16.
- Responders, defined as achieving IGA (0,1) or EASI-75 at Week 16, will receive 250 mg SC Q4W.
- Inadequate responders at Week 16 will continue to receive 250 mg SC Q2W.

The study population is described in Section 5.

The efficacy and safety assessments are described in Sections 8.1 and 8.2, respectively.

### 4.2. Scientific Rationale for Study Design

There is a paucity of data to guide diagnosis and treatment in populations traditionally under-represented in clinical trials, including patients with skin of color. The present study will evaluate the safety and efficacy of the skin of color population with clinical assessment methods suitable for this population to complement the already existing data on racial subgroups from the lebrikizumab clinical programs. Clinical studies (Phase 2a Study GS29250 and Phase 2b Study DRM06 AD01) with lebrikizumab demonstrated significant clinical benefit in participants with AD. Additional detailed discussion of the lebrikizumab studies is provided in the lebrikizumab IB. The top-line results from 2 randomized controlled monotherapy Phase 3 studies of lebrikizumab (ADvocate 1 and ADvocate 2) and a third completed Phase 3 trial of lebrikizumab in combination with topical steroids (ADhere) demonstrated positive risk benefit in adult and adolescent patients with moderate-to-severe AD at Week 16. Additional detailed discussion of the lebrikizumab studies is provided in the lebrikizumab IB. Since randomized controlled data are already available, this study will be conducted as an open-label study to mimic the real-world

experience. We will use Week 16 as the primary endpoint in this study and will also evaluate the safety and efficacy until Week 24 to understand the durability of effect post Week 16.

In this study, collection of demographic information includes race and ethnicity. The scientific rationale is based on the need to assess variable response in safety and efficacy based on race or ethnicity. This question can be answered only if all the relevant data are collected.

#### **4.2.1. Participant Input into Design**

Throughout this protocol, the term “participant” is used to indicate an individual who participates in a clinical trial, either as a recipient of an investigational drug or as a control. This usage reflects preferences indicated by patient advocates to more accurately reflect the role of people who take part in clinical trials.

No participant input was provided for this study design.

### **4.3. Justification for Dose**

The lebrikizumab dosing regimen of 500 mg loading dose at baseline and Week 2, followed by 250 mg Q2W up to, and including Week 16, was selected based on an evaluation of safety, efficacy, and PK data from the Phase 2 and Phase 3 lebrikizumab trials.

In the lebrikizumab Phase 3 programs, IGA 0/1 or EASI-75 responders at Week 16 were re-randomized to Q4W, Q2W, or withdrawal arms, and inadequate responders were assigned to Q2W dosing. These Phase 3 results have demonstrated that lebrikizumab Q4W and Q2W are similar in efficacy, and that inadequate responders benefited from continued Q2W dosing. The dose regimens in the present study post Week 16 are based on the results of these Phase 3 studies.

#### **Adolescent Participants**

In this Phase 3b study, adolescent participants ( $\geq 12$  to  $< 18$  years weighing  $\geq 40$  kg) will be included and will receive the same doses of lebrikizumab as adult participants. Pharmacokinetic analyses of SC doses of lebrikizumab reveal similar kinetics for adults and adolescents  $\geq 12$  to  $< 18$  years. Although maximal exposures are slightly higher for any given dose in adolescent participants, due to their lower weight ranges, the safety profile observed in adolescent participants is comparable to the safety profile observed in adults. Therefore, a similar exposure-response relationship is expected in this age group compared to adults based on partial extrapolation and propose to include adolescent participants in this study. It is expected that the adolescent AD participants  $\geq 40$  kg will demonstrate a similar overall safety profile as adult participants.

